#### 13.1 CHARTERS AND RETENTION PLAN TO PREVENT MISSING DATA

#### 13.1.1 CEC Charter

Final CEC Charter

## 13.1.2 DMC Charter and Integrity Charter

Final DMC Charter and Integrity Charter

## 13.1.3 Retention Plan to prevent missing data

[figure not shown]
Final Retention Plan to Prevent Missing Data

## 13.1.4 Conversion to Type II Diabetes Adjudication Charter

[figure not shown]
Final Clinical Events Committee Diabetes Adjudication Charter

[figure not shown]
#### 13.2 DIAGRAMS OF CENSORING ALGORITHMS

[figure not shown]
## 13.2.1 Censoring at Interim Analysis

## 13.2.2 Censoring at Study Completion

#### 13.3 ADVERSE EVENT START AND END DATE IMPUTATION ALGORITHM

#### **Description of Incomplete**

End Date Imputed date

Day missing (YearMonth only) and Date of Death is not missing

YearMonth earlier than

YearMonth of  $\underline{\text{Date of Death}} \longrightarrow \text{Impute to the last day of the month}$ 

YearMonth equals YearMonth

of Date of Death  $\rightarrow$  Date of Death

Month missing (Year) and Date of Death is not missing

Year earlier than Year of Date

of Death → Impute to the last day of the year

Year equals Year of Date of

 $\underline{\text{Death}} \longrightarrow \underline{\text{Date of Death}}$ 

ALL is missing and Date of Death is not missing

→ Date of Death

Day missing (YearMonth) and Date of Death is missing

YearMonth Impute to the last day of the month

Month missing (Year) and Date of Death is missing

Year → Impute to the last day of the year

ALL is missing and Date of Death is missing

→ No imputation

# **Description of Incomplete**

Start Date Imputed date

## Day missing (YearMonth

Only)

YearMonth earlier than

YearMonth of  $\underline{\text{First Dose Date}} \longrightarrow \text{Impute to first of the month}$ 

YearMonth equal YearMonth

of First Dose Date → Impute to First Dose Date or AE End Date, whichever is earlier

YearMonth greater than

YearMonth of First Dose Date → Impute to first of the month

Month missing (Year)

Year earlier than Year of First

Dose Date → Impute to first of the year

Year equal Year of First Dose

Date → Impute to First Dose Date or AE End Date, whichever is earlier

Year greater than Year of  $\underline{First} \rightarrow Impute to first of the year$ 

Dose Date	
ALL is missing	
	Impute to First Dose Date (or randomization date for subjects who did
	→ take study treatment) or AE End Date, whichever is earlier

#### 13.4 CONCOMITANT MEDICATION START AND END DATE IMPUTATION ALGORITHM

There is clear evidence the drug was STOPPED BEFORE the Screening Visit (from Prior Meds page)

### **Description of Incomplete End Date**

## Imputed date

Day missing (YearMonth) and Date of Screening is not missing YearMonth earlier than YearMonth of Date of			
Screening	$\rightarrow$	Impute to the last day of the month	
YearMonth equals YearMonth of Date of Screening	$\rightarrow$	Date of Screening	
Month missing (Year) and Date of Screening is not missing			
Year earlier than Year of Date of Screening	$\rightarrow$	Impute to the last day of the year	
Year equals Year of Date of Screening	$\rightarrow$	Date of Screening	
ALL is missing and Date of Screening is not missing			
	$\rightarrow$	Date of Screening	

## There is **NO** clear evidence the drug was **STOPPED BEFORE** the Screening Visit

### **Description of Incomplete End Date**

### Imputed date

Day missing (YearMonth only) and Date of Death is not missing YearMonth earlier than YearMonth of Date of				
Death	$\rightarrow$	Impute to the last day of the month		
YearMonth equals YearMonth of Date of Death	$\rightarrow$	Date of Death		
Month missing (Year) and Date of Death is not missing				
Year earlier than Year of Date of Death	$\rightarrow$	Impute to the last day of the year		
Year equals Year of Date of Death	$\rightarrow$	Date of Death		
ALL is missing and Date of Death is not missing				
	$\rightarrow$	Date of Death		
Day missing (YearMonth) and Date of Death is missing				
YearMonth		Impute to the last day of the month		
Month missing (Year) and Date of Death is missing				
Year	$\rightarrow$	Impute to the last day of the year		
ALL is missing and Date of Death is missing				
	$\rightarrow$	No imputation		

## **Description of Incomplete**

Start Date Imputed date

Day missing (YearMonth	
Only)	
YearMonth earlier than	
YearMonth of First Dose Date	→ Impute to first of the month
YearMonth equal YearMonth	
of First Dose Date	→ Impute to First Dose Date or Med End Date , whichever is earlier
YearMonth greater than	
YearMonth of First Dose Date	→ Impute to first of the month
Month missing (Year)	
Year earlier than Year of First	
Dose Date	→ Impute to first of the year
Year equal Year of First Dose	Impute to First Dose Date(or randomization date for subjects who did
Date	→ take study treatment) or Med End Date, whichever is earlier
Year greater than Year of First	
Dose Date	→ Impute to first of the year
ALL is missing	
	→ Impute to First Dose Date or Med End Date , whichever is earlier

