Phase	Pre-randomization	Randomization																		
Period	Screening	Treatment																	F/U	
Visit	1	2 ^a	3	4	5	6	7	8	9	10	11	12	13	14	15	16	17	EOT	EOS	Unsch ^b
Month ^c	Days -30 to -1	Day 1	3	6	9	12	15	18	21	24	28	32	36	40	44	48	52	56		
Assessment (revised per Amendment 01)																				
Study drug dispensing ^e		X	X	X	X	X	X	X	X	X	X	X	X	X	X	X	X	X		
Collect study medication ^e			X	X	X	X	X	X	X	X	X	X	X	X	X	X	X	X	X	
Drug accounting & compliance ^e			X	X	X	X	X	X	X	X	X	X	X	X	X	X	X	X	X	
AE monitoring ⁱ	<----->																			
MACE/MACE+ reporting ⁱ	<----->																			

(revised per Amendment 01)

Notes: Upon Sponsor Notification of Study Completion (ie, trial completion), sites will be instructed to bring subjects who remain on treatment for an EOT visit. An EOS visit will occur approximately 30 days later for subjects on treatment at Sponsor Notification of Study Completion.

Subjects who prematurely discontinue study drug are to complete the EOT visit within approximately 30 days, and will continue in the study for all subsequent study visits until study completion. If the next scheduled visit after EOT assessments is <30 days, subjects can skip that visit and return for the next subsequent visit (eg, if the EOT is 15 days prior to the scheduled Month 36 visit, they can skip Month 36, and come in at Month 40). All procedures and assessments should be performed at subsequent visits until EOS except where footnoted in assessment column. Upon Sponsor Notification of Study Completion, subjects who prematurely discontinued study medication ≥30 days before will return for an EOS visit. Subjects who are still being followed in the study but who discontinued study medication within 30 days of Sponsor Notification of Study Completion will return for an EOS visit approximately 30 days after their last dose of study medication.

ACR = albumin-to-creatinine ratio; AE = adverse event, ECG = electrocardiogram, EOS = end of study; EOT = end of treatment; F/U = Follow-up; HbA_{1c} = glycosylated hemoglobin, hsCRP = high sensitivity C-reactive protein; incl. = including; IxRS = interactive voice and/or web response system; MACE = major adverse cardiovascular events; MACE+ = MACE or hospitalization for unstable angina or heart failure, and any coronary revascularization; PGx = pharmacogenomics, Unsch = unscheduled.

- a. Visit 2 = Baseline/Randomization. The first dose should be taken at this visit. (revised per Amendment 01)

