#### 8 DEFINITIONS AND CONVENTIONS FOR DATA HANDLING

The baseline value for efficacy and safety will be defined as the most recent value reported prior to or at randomization. Adverse events with missing severity will be assigned the highest severity. Adverse events with missing relationship will be assigned as related, as part of a sensitivity analysis. Adverse events and Concomitant Medications with partial dates will be imputed according the algorithm defined in the SDTM specifications, also included in Appendix 13.6.

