    - o random plasma glucose > or = 200 with associated symptoms of hyperglycemia prior to or at Baseline
- Subject who are Pre-diabetic at Baseline: Subject must meet all the following conditions;
  - o On the Diabetes History Form "Clinical diagnosis of diabetes?" = "No" and
  - o Not initiated any diabetes treatment prior to or at Baseline and
  - At least one of the following:
    - o HbA1c 5.7% to <6.5% or
    - FPG 100 to 125 mg/dL (5.55 to 6.94 mmol/L) between Screen and Baseline and
  - None of the following where available
    - o HbA1c  $\geq$  6.5% in all central or local labs assessments prior to or at Baseline and
    - o FPG ≥ 126 mg/dL (7.0 mmol/L) in all central or local labs assessments prior to or at Baseline and
    - o random plasma glucose > or = 200 with associated symptom of hyperglycemia prior to or at Baseline and
    - o 2-hour plasma glucose ≥ 200 mg/dL(11.1mmol/L) by an OGTT test prior to or at Baseline and
- Subject who are Normoglycemic at Baseline: Subject must meet the following conditions:
  - o On the Diabetes History Form "Clinical diagnosis of diabetes?" = "No" AND
  - o Not initiated any diabetes treatment prior to or at Baseline AND
  - o None of the following where available:
    - o HbA1c  $\geq$  5.7% in all central or local labs assessments prior to or at Baseline

- o FPG ≥ 100 mg/dL (5.55 mmol/L) in all central or local labs assessments prior to or at Baseline
- 2-hour plasma glucose ≥ 200 mg/dL(11.1mmol/L) by an OGTT test prior to or at Baseline
- Random glucose > or = 200 with associated symptoms of hyperglycemia prior to or at Baseline
- Subject is not otherwise defined as 'pre-diabetic' at baseline
- Subjects who are T2DM at Baseline: Subject must meet at least one of the following conditions.
  - o On the Diabetes History Form "Clinical diagnosis of diabetes?" = "Yes" and Type of Diabetes = 2 on Diabetic History CRF or
  - o HbA1c  $\geq$  6.5% prior to or at Baseline in either central or local labs or
  - o FPG ≥ 126 mg/dL (7.0 mmol/L) prior to or at Baseline in either central or local labs or
  - o 2-hour plasma glucose  $\geq 200 \text{ mg/dL}(11.1 \text{mmol/L})$  by an OGTT test or
  - Random plasma glucose > or = 200 with associated symptoms of hyperglycemia prior to or at Baseline
  - o Any diabetes treatment prior to or at Baseline
- Subjects who are T1DM at Baseline: Subject must meet the following conditions.

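### Three patterns of incomplete medication start date are imputed to first dose, which falls at Baseline, so an antidiabetic drug started on study could reclassify a prediabetic subject as T2DM at Baseline

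*SAP*

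**What the plan says.** **Imputation.** SAP 13.4 gives the rules for incomplete medication start dates. Three patterns go to the first dose date, or to the medication end date if that is earlier:

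- the day is missing and the month is the first-dose month;
- the month is missing and the year is the first-dose year (this branch reads "Impute to First Dose Date(or randomization date for subjects who did" and continues with the end-date alternative);
- the branch headed "ALL is missing".

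A known later month goes to the first of that month. A known later year ("Year greater than Year of First" dose) goes to the first of that year. The end-date rules in 13.4 first ask whether the drug is known to have stopped before Screening. The start-date rules have no matching question about whether the drug began after Baseline.

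**Scope.** SAP Section 8 applies the imputation generally: "Adverse events and Concomitant Medications with partial dates will be imputed according the algorithm defined in the SDTM specifications". It makes no exception for antidiabetic drugs or for baseline classification. (It points to Appendix 13.6; the medication algorithm stands at 13.4.)

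**Baseline status.** In the Section 8 definitions, "any diabetes treatment prior to or at Baseline" is one of several conditions for T2DM at Baseline, and any one of them suffices. Both the prediabetes definition and the without-any-diabetes definition require "Not initiated any diabetes treatment prior to or at Baseline".

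**Timing.** Protocol Table 4, footnote a: "Visit 2 = Baseline/Randomization. The first dose should be taken at this visit".

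**Use.** The key secondary analysis, time to conversion to T2DM, runs in the Prediabetes Analysis Set (SAP 5.4.2). The Nondiabetes and T2DM sets, also defined through Section 8, carry secondary glycemic and renal analyses (SAP 5.4.3).

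**The concern.** Imputing an unknown start date to first dose is an ordinary convention for medication tables, because it keeps the drug in the concomitant column. It is unsuitable for deciding who was already treated at Baseline. A drug first prescribed months into the trial acquires a Baseline date, and that date alone is enough to class the subject as T2DM at Baseline.

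The drugs at issue are closely tied to the endpoint. Protocol 9.4.7.2 allows diabetes drugs to be started on study, and the endpoint definition (SAP 5.1.2) waives confirmatory testing for subjects put on treatment after an abnormal result. Converters are therefore a natural group to have such a record. The conversion itself is adjudicated and dated from the first abnormal laboratory test (SAP 8.5.2.2). A sound event could thus drop out of the analysis because of an incomplete date on a different form.

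At stake is whether membership of the key secondary analysis set is fixed by baseline information. Conversions lost this way lower the observed rate in the Prediabetes and Nondiabetes sets, and the same subjects enter the T2DM set used for 6-month HbA1c and renal outcomes. The Table 2 subgroups by baseline diabetic and cardiovascular medication are open to the same misdating.

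**Working it through.** **1. The rule applied to examples.** Take first dose on 10 March 2014 and an antidiabetic drug started afterwards:

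| Recorded start | Imputed start | Section 8 result |
|---|---|---|
| March 2014, day missing | 10 Mar 2014 | at Baseline: T2DM |
| 2014, month missing | 10 Mar 2014 | at Baseline: T2DM |
| nothing recorded | 10 Mar 2014 | at Baseline: T2DM |
| October 2014, day missing | 1 Oct 2014 | after Baseline: unaffected |
| 2016, month missing | 1 Jan 2016 | after Baseline: unaffected |

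Three of the five patterns reclassify the subject. Beyond the first-dose calendar year, only a wholly missing date does so. If first dose falls after the randomization day, the imputed date also falls after Baseline and the error does not arise.

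**2. The plan's own figure.** Inputs from SAP Section 4: 457 events, hazard ratio 0.75, two-sided 0.05, about 33% of 12,000 (3,960 subjects), 4% per year, 15-month accrual, 54 months, 5% annual dropout.

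Power = Φ(√d/2 × |ln 0.75| − 1.96). With d = 457: 10.689 × 0.2877 − 1.96 = 1.115, so power is 86.8%. The plan states 86%, so the figure is reproduced.

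Expected events per arm = 1,980 × the mean, over follow-up of 3.25 to 4.5 years, of λ/(λ+0.05) × [1 − exp(−(λ+0.05)t)]. With λ = 0.04 and 0.03 this gives 258.8 + 197.7 = 456.5, against the planned 457.

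**3. Loss of conversions.** The share lost is an assumption, because the documents give no rate of incomplete dates.

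| Share lost | Conversions lost | Events left | Power |
|---|---|---|---|
| 0% | 0 | 457 | 86.8% |
| 1% | 5 | 452 | 86.4% |
| 5% | 23 | 434 | 85.0% |
| 10% | 46 | 411 | 83.1% |

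If both arms lose the same share, the hazard ratio barely moves. In events, 195.9/261.1 = 0.75. After a 5% loss in each arm, 186.1/248.1 = 0.75.

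**4. Exposure under the month-missing rule.** The average rate is (4% + 3%)/2 = 3.5% per year. With about half a year from first dose to 31 December, 3,960 × 0.035 × 0.5 = about 69 conversions fall in the first-dose calendar year. Using the plan's rates with enrolment starting in December 2013 or January 2014, and drug start coinciding with conversion, the share is 15–17% of 457, or 71–77. If every one of these were lost, 380–386 events would remain and power would be about 80–81%.

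Protocol Table 4 schedules the first post-baseline HbA1c at Month 3 and the first FPG at Month 6. Counting only what those tests can detect before year end, with first doses spread evenly over the year, mean exposure is (3/12 × 3) + (6/12 × 6) = 3.75 months. That gives 3,960 × 0.035 × 3.75/12 = about 43.

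The day-missing rule reaches about 1.3% of conversions (0.013 × 457 = about 6), and no glycemic test is scheduled in the first month.

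**The case against.** The strongest objection is that the central link is inferred. No sentence says that imputed dates determine baseline glycemic status. Section 8 attributes the algorithm to the SDTM specifications, and SAP Section 9 leaves derivation rules to separate documents that are not available here. Baseline treatment is also collected directly: Protocol 9.4.7 requires T2DM drugs from the 90 days before first dose to be recorded, and Protocol 9.5.1.2 requires diabetes history at Screening. A careful programmer could use those sources. This stands as a limit, and the point is therefore conditional. It does not remove the point: the written rules permit the error, nothing in either document prevents it, and two programmers could build different Prediabetes sets.

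Three stronger readings are tempting, and the documents do not support them.

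- *All incomplete start dates revert to Baseline.* They do not. Known later months and years stay after it. Medications are reviewed at every visit, so many records should carry at least that much.
- *About 70 conversions will be lost.* That figure is a ceiling on exposure to one rule. A loss also needs drug treatment in the same calendar year and a start month that stays missing after data cleaning.
- *The hazard ratio is biased.* Losing five conversions from one arm only would move 0.75 to 195.9/256.1 = 0.76 (placebo) or 190.9/261.1 = 0.73 (lorcaserin). But the trial is double-blind, adjudication is blinded, and nothing suggests that date completeness differs by arm.

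**Conclusion.** The point holds in conditional form. If imputed start dates feed the Section 8 definitions, an antidiabetic drug started on study with one of three incomplete-date patterns takes the subject and any conversion out of the Prediabetes and Nondiabetes sets and puts the subject in the T2DM set. Analysis-set membership would then rest on information that arose after randomization.

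The numerical effect is probably small and cannot be sized from the documents. Even an assumed 10% loss costs under four points of power (86.8% to 83.1%), and with similar loss in both arms the cost is events rather than bias in the hazard ratio. The conclusion also assumes that first dose is taken on the randomization day, as the protocol directs.

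The reason to act is the principle that a key secondary analysis set should not depend on follow-up data. The rules as written give a wrong classification for a definable set of records, so this is more than a missing detail.

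**What to change.** State in SAP Section 8 and 13.4 that imputed start dates are not used to decide baseline glycemic status or the Table 2 baseline-medication subgroups. Count a drug as baseline treatment only if it is recorded as prior or ongoing at Screening/Visit 2, or if the known part of its start date lies wholly on or before randomization. Otherwise treat it as started after randomization. Keep the present imputation for the medication tables.

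The cost is a short SAP statement and one change to the baseline-classification program, using data already collected. The downside is that a few subjects truly treated at Baseline, but with undocumented dates, could remain in the Prediabetes set. The Diabetes History form and the HbA1c and FPG criteria in Section 8 would catch most of them.
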